**NCTo2540629**

**08/06/2015**

## Study protocol

### Study design and Setting

This study was a before and after study of the implementation of a bundle of UTIS CPR programs in Seoul Metropolitan City. The before phase was defined as January 2013 through December 2014 and included a historic control population. The after phase was defined as January 2015 through December 2016.

Seoul has approximately 10 million inhabitants per 605 km^2. The SMFD provides fire-based and public service under 24 EMS agencies with 140 ambulances with a single unified dispatch center, with approximately 300,000 transports per year including 4,800 OHCAAs. EMS providers can provide care comparable to an intermediate emergency medical technician (EMT-I) level in the United States. EMTs cannot declare death or stop CPR in the field unless a return of spontaneous circulation (ROSC) occurs. Therefore, all patients with OHCA are transported to emergency departments (EDs) while receiving CPR in an ambulance. The EMS CPR protocols were revised on the 2010 and 2015 International guidelines.

In Seoul, a DACPR program was implemented in 2010 and has been in effect for all calls suspected to involve cardiac arrest. The dispatch center has a standard protocol for DACPR with two steps; 1) screening potential OHCAAs by primary call dispatcher (PCD) and 2) providing telephone CPR instruction by medical call dispatcher (MCD). Prior to 2015, Seoul was covered by a single-tiered EMS service to respond to OHCA events. A nearest and available ambulance was dispatched to an OHCA event. Of the 140 ambulances, only 27 (23.3%) were equipped with a defibrillator with a feedback function until December 2014. However, there was no active feedback CPR training as a feedback to EMTs after review of the CPR records by medical directors.

### Intervention

A bundle of three UTIS CPR programs were implemented in Jan. 2015; 1) a high-quality DACPR program, 2) a rapid dispatch program using MTR, and 3) an FCPR program using defibrillators with feedback functions. A high-quality DACPR program was implemented in 2015 in addition routine DACPR program. This program included monthly monitoring and evaluation of the quality of the call

receiving and consulting stages by a medical director. Ten percent of the calls correctly identified as cardiac arrest and 10% of the calls not recognized as cardiac arrest were randomly selected based on the records from the ambulance run sheet. The audit reviews were performed in a standardized manner and recorded on an audio review evaluation sheet. Performance standard indicators were set, and feedback for the executive members, including the dispatch center officers and medical directors during the study period. Key performance standard indicators included OHCA detection rate by the PCD and proportion of calls given CPR instructions within 120 seconds. Monthly education conferences for dispatchers were conducted to get feedback of the performance standards per individual and per dispatch teams. The rapid CPR program included a multi-tier response (MTR) using the nearest available fire engine or basic life support vehicle team in addition to routine ambulance dispatch. An MTR scene protocol was developed, and a train-the-trainer model was used to disseminate the protocol. Six education programs were conducted, and 141 (10.8% of all the EMS providers in Seoul) participants from 24 EMS agencies were trained as trainers in 2015. They conducted MTR CPR training programs for all the EMTs and firefighters in Seoul. The FCPR program included the distribution of defibrillators with feedback functions to each ambulance and EMT training program; EMS personnel were also strongly encouraged to use a defibrillator with a feedback function for professional recording of EMS-CPR, and the medical director provided feedback to the individual teams using these defibrillators. All CPR processes were recorded by these devices and uploaded by the EMTs after CPR to an electronic server of the SMFD to be reviewed by the EMS medical directors. The MTR was a newly implemented program, but the other two programs were incomplete before 2015. It is a new attempt in this study to try to apply both programs (DACP and FCPR) robustly and systematically to the whole city EMS.

#### Data sources and collection

We used the Korean OHCA Registry of by the Korea Centers for Disease Control and Prevention (CDC), which captures all incident cases of OHCA in the Seoul, was retrieved from the following four sources: the EMS run sheets for basic ambulance operation information, the EMS CPR registry, the dispatcher CPR registry, and the hospital OHCA registry for hospital care and outcomes. The medical record reviewers from the Korea CDC extracted the recorded information on the cause of arrest, hospital care

and outcomes from approximately 700 hospitals. To ensure the quality of the medical record review process, a quality management committee of emergency physicians, epidemiologists, statistical experts, and medical record review experts analyzed the data every month while providing feedback to each medical record reviewer.

#### Study population

Patients with OHCA of presumed cardiac etiology who were 15 years of age or older and who used the EMS system in Seoul between January 2013 and December 2016 were included. Patients were excluded from the analysis if they did not receive resuscitative attempts, had their episode witnessed by EMS providers, or occurred at a primary care clinic or long-term care facility. Patients with missing information on neurologic outcomes at the time of discharge were also excluded.

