#### Main outcomes

The primary outcome was good neurologic recovery at discharge from the hospital, which was defined as having a cerebral performance categories (CPC) score of 1 or 2. The secondary outcome was survival to hospital discharge. The tertiary outcome was the prehospital return of spontaneous circulation (ROSC). The reviewers who were employed at the Korea CDC visited approximately 700 hospitals and extracted the final treatment results using the medical records of the doctors and nurses and the final discharge summary.

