#### Sample size calculation

There were not enough previous studies available to determine the sample size needed to evaluate the effectiveness of the Utstein CPR program bundle. Prior to the initiation of the study, the sample size was estimated assuming a survival rate of 9% during the control period and an 11% survival rate during the experimental period. For each group of patients, 4,035 were needed to assess significant differences based on 80% of power and 0.05 of alpha.

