#### Statistical analysis

The demographic findings and survival outcomes of the study population by study period are compared. The continuous variables were compared using the Wilcoxon rank sum test and the categorical variables were compared using the chi-squared test. The temporal trends by study period with six-month interval on performance indicators for each intervention were evaluated by the Cochran-Armitage test for the trends. We calculated the absolute differences (AD) with 95% confidence intervals (CIs) of the outcomes between the study periods and between the patient groups receiving each CPR program. A mixed-effects logistic regression model using the GLIMMIX procedure was used to estimate the association between the study period with outcomes, adjusting for the following: demographics (Model 1); demographics, community factors, and EMS factors (Model 2); demographics, community factors and EMS factors, and post-resuscitation care factors (Model 3); and finally, demographics, community factors and EMS factors, ACLS factors, and post-resuscitation care factors (Model 4). Outcomes were compared to assess the overall effect of all programs administered to patients before and after intervention. To assess the

individual effects of each program, a multi-variable logistic regression analysis was performed to evaluate the association between individual programs and outcomes. We constructed a mixed-effects logistic regression model to test the association between each CPR program (DACPR, MTR, and FCPR) and outcomes that was adjusted for potential confounders. We included random intercepts for ambulance station to control for clustering within the ambulance stations in both models. The effect sizes were calculated with AOR and 95% CIs. The p value was set at 0.05, and all statistical tests were 2-tailed. All statistical analyses were performed using the SAS version 9.4 software (SAS Institute Inc., Cary, NC, USA) and R version 3.4.1 (available at <https://www.rproject.org>. accessed on Feb. 25, 2018).

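### Patients without a discharge neurologic score are dropped from every analysis, including prehospital ROSC and survival, which do not need that score

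*Combined protocol and SAP*

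**What the plan says.** The Study population section first lists its exclusions as applying to the analysis as a whole ("Patients were excluded from the analysis if they did not receive resuscitative attempts") and then adds: "Patients with missing information on neurologic outcomes at the time of discharge were also excluded". No separate analysis set is defined for any outcome, there or under Statistical analysis.

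Under Main outcomes, the primary outcome is good neurologic recovery at discharge, "which was defined as having a cerebral performance categories (CPC) score of 1 or 2". The other two outcomes follow: "The secondary outcome was survival to hospital discharge. The tertiary outcome was the prehospital return of spontaneous circulation (ROSC".

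Data sources and collection names the EMS run sheets and then "the EMS CPR registry, the dispatcher CPR registry, and the hospital OHCA registry for hospital care and outcomes". A quality committee "analyzed the data every month while providing feedback to each medical record reviewer". No completeness figure is given.

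Statistical analysis plans period comparisons by mixed-effects logistic regression and also absolute differences: "We calculated the absolute differences (AD) with 95% confidence intervals (CIs) of the outcomes between the study periods". It is silent on missing outcomes.

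**The concern.** The rule raises two separate problems.

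- **Unneeded loss of data.** Prehospital ROSC happens before hospital arrival, and survival can be known without a CPC grade. A patient with either outcome recorded is removed because a different variable is blank. This is so whatever the missing rate.
- **Possible selection on outcome.** A patient known to have died cannot be CPC 1-2, so the primary outcome is settled without further grading. Those who cannot be classified are survivors without a CPC, or patients with untraced discharge status. If survivors are over-represented among them, the exclusion lowers observed survival, and perhaps ROSC.

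If that loss differs between periods, the before/after contrast is biased, in either direction. Without counts by period and vital status, a reader cannot tell whether the effect is nil or material.

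**Working it through.** **Inputs from the documents.** The sample size section gives the scale: "assuming a survival rate of 9% during the control period and an 11% survival rate during the experimental period", a difference of 2 points, with 4,035 patients per period, 80% power and alpha 0.05. From those inputs a two-sided comparison of proportions gives 3,531 per period, or 3,631 with continuity correction. The stated 4,035 follows only if 10% loss is added (3,631 / 0.90 = 4,034.4, rounded up), an allowance the plan does not mention. Nothing below depends on it.

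**Assumptions.** The documents give no missing rates. All rates below are illustrative, with the before period listed first.

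**1. Survival when missingness differs between periods.** Let s be true survival, m the share of all patients with missing CPC, and f the share of those who are survivors.

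Observed survival = (s − f·m) / (1 − m), with s = 0.10 in both periods:

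| m before / after | f | Observed before | Observed after | False difference |
|---|---|---|---|---|
| 0.2% / 0.1% | 1 | 9.82% | 9.91% | +0.09 points |
| 1.0% / 0.3% | 0.5 | 9.60% | 9.88% | +0.28 points (OR 1.03) |
| 1.0% / 0.3% | 1 | 9.09% | 9.73% | +0.64 points (OR 1.08) |
| any | 0.10 (= s) | 10% | 10% | 0 |
| equal m, same f | any | equal | equal | 0 |

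Example, third row: (0.10 − 0.010) / 0.990 = 0.0909 and (0.10 − 0.003) / 0.997 = 0.0973. Swapping the two missing rates reverses the sign. With survival at 10%, this row means that 10% of survivors lack a CPC before (0.010 / 0.10) and 3% after (0.003 / 0.10).

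**2. Primary outcome.** Let g = 0.05 be the true CPC 1-2 rate in both periods, with all missing patients survivors and a share p of them truly CPC 1-2.

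Observed rate = (g − p·m) / (1 − m):

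| m before / after | p = 0 | p = 0.5 | p = 1 |
|---|---|---|---|
| 0.2% / 0.1% | −0.01 | +0.05 | +0.10 |
| 1.0% / 0.3% | −0.04 | +0.32 | +0.67 |

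Entries are false differences in percentage points. Example, lower right: (0.05 − 0.010) / 0.990 = 0.0404 and (0.05 − 0.003) / 0.997 = 0.0471.

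**3. Survival when the same fraction q of survivors is missing in both periods.** Observed survival = s(1 − q) / (1 − s·q), with true rates of 9% and 11%:

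- q = 0: difference 2.00 points, OR 1.25.
- q = 3%: 8.75% and 10.71%, difference 1.95 points, OR 1.25.
- q = 10%: 8.17% and 10.01%, difference 1.84 points, OR 1.25.

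The crude odds ratio is unchanged; the absolute difference shrinks.

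**4. Bounds.** Suppose a share m is missing in each period and the analysed patients show 9% and 11%. The worst-case and best-case differences are 0.02(1 − m) − m and 0.02(1 − m) + m:

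- m = 1%: +1.0 to +3.0 points.
- m = 2%: about 0.0 to +4.0 points.

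Distortion of ROSC cannot be quantified, because the documents give no ROSC rate and no link between ROSC and missing CPC.

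**The case against.** The strongest reply is that no harm is shown. One registry, one body of record reviewers and a monthly quality committee cover both periods. The bundle changed dispatch, response and defibrillators, and nothing suggests that discharge abstraction changed. The larger scenario needs 10% of survivors ungraded before and 3% after, which the documents do not support. At 4,035 per period, the standard error of the survival difference is √[(0.09·0.91 + 0.11·0.89) / 4,035] = 0.67 points. A shift of 0.09 points is therefore small and one of 0.64 is about one standard error. The planned effect measure is an adjusted odds ratio. If loss depends only on survival status, and equally in both periods, the survival odds ratio is preserved, approximately so in the mixed model. CPC and survival come from the same hospital records, so an untraced patient lacks both. A single cohort complete on the primary outcome is also a recognised choice that keeps denominators the same.

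Much of this stands. Size and direction are unknown, missingness may be trivial, and the proposed change recovers untraced patients only for ROSC and for the bounds. The documents also do not say which source supplies ROSC; that it comes from EMS records is an inference.

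It does not rescue the rule. Equal completeness across periods is as undocumented as unequal completeness. The absolute differences move even when the odds ratio does not. Consistent denominators are a weak reason to discard a recorded ROSC or survival status on a criterion measured after the intervention and tied to the outcome.

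**Conclusion.** The concern holds. The plan applies a filter on the primary outcome's completeness to all three outcomes, two of which do not need it, and provides no means of judging the consequence. The unneeded exclusion is clearest for prehospital ROSC. For survival, it applies to patients whose discharge status is recorded.

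Selection on outcome is possible but not demonstrated. Under the assumed rates, the false survival difference runs from 0 to 0.64 points, up to about a third of the planned 2 points (0.64 / 2 = 0.32). For the primary outcome it runs from −0.04 to +0.67 points. The signs reverse if the missing rates are reversed. There is no bias if missingness is unrelated to outcome. This is a change that should be made because it is cheap and the risk cannot be excluded; it is not evidence that the result is wrong.

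**What to change.** 1. Remove missing neurologic outcome from the exclusions under Study population.
2. Analyse prehospital ROSC and survival to discharge in all eligible patients with that outcome recorded.
3. For the primary outcome, state that known deaths count as not CPC 1-2, so that only survivors without a CPC and untraced patients are missing.
4. Report the number with missing CPC by period and vital status.
5. Give best-case and worst-case bounds for the between-period difference. If missingness is not trivial, multiple imputation of CPC among survivors is an optional addition.

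The cost is revised wording and a modest amount of extra analysis on registry data already held. Denominators may differ slightly between outcomes, and each table should state its own.

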#### Main outcomes

The primary outcome was good neurologic recovery at discharge from the hospital, which was defined as having a cerebral performance categories (CPC) score of 1 or 2. The secondary outcome was survival to hospital discharge. The tertiary outcome was the prehospital return of spontaneous circulation (ROSC). The reviewers who were employed at the Korea CDC visited approximately 700 hospitals and extracted the final treatment results using the medical records of the doctors and nurses and the final discharge summary.

#### Variables and measurement

Bystander CPR was categorized into the following 3 groups: bystander CPR with dispatcher assistance group, bystander CPR without dispatcher assistance group, and no bystander CPR group. The MTR was positive if more than 2 vehicles arrived to cases with the same accident number. There were two types of MTR including an ambulance-tiered response (ATR) and a fire-engine-tiered response (FTR). FCPR was considered as positive if the corresponding ambulance used a defibrillator with feedback function. We collected following variables 1) demographics (age, gender, past medical history (diabetes mellitus, hypertension, heart disease, and stroke), event date and time (season, weekend, daytime)), 2)

community factors (location of arrest (public vs. private vs. other), witness status, primary cardiac rhythm at the scene (shockable, PEA and asystole), and bystander CPR or defibrillation), 3) EMS factors (EMS defibrillation, prehospital advanced airway, fluid resuscitation, mechanical CPR device use, detection time interval from call to detection of OHCA by the dispatcher, and EMS time intervals (response time interval, scene time interval, and transport time interval), and 4) post-resuscitative care (cardiac reperfusion therapy, targeted temperature management, and extracorporeal membrane oxygenation (ECMO)).

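### MTR is coded positive only when more than two vehicles arrive, but the intervention it measures is one vehicle added to the routine ambulance

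*Combined protocol and SAP*

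**What the plan says.** Three sections bear on how many vehicles make an MTR.

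- **Study design and Setting** gives the starting point: "Prior to 2015, Seoul was covered by a single-tiered EMS service to respond to OHCA events", and "A nearest and available ambulance was dispatched to an OHCA event". The routine response is one ambulance.
- **Intervention** describes the MTR program as a response "using the nearest available fire engine or basic life support vehicle team in addition to routine ambulance dispatch". One unit is added to the routine one.
- **Variables and measurement** gives the only operational rule: "The MTR was positive if more than 2 vehicles arrived to cases with the same accident number". The next sentence divides MTR into an ambulance-tiered and a fire-engine-tiered type and does not restate the count.

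**Statistical analysis** then uses MTR as an exposure. Absolute differences are calculated "between the study periods and between the patient groups receiving each CPR program", and a mixed-effects logistic model is built to "test the association between each CPR program (DACPR, MTR, and FCPR) and outcomes that was adjusted for potential confounders". The same section adds: "The temporal trends by study period with six-month interval on performance indicators for each intervention were evaluated by the Cochran-Armitage test". It does not say whether the MTR flag is one of those indicators.

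**The concern.** The exposure definition excludes the basic form of the exposure. One ambulance plus one added vehicle is two, and two is not more than two. An analyst who programs the variable from this text would place ordinary MTR responses in the comparison group with single-ambulance responses, and only larger responses would count as MTR.

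The MTR absolute difference and adjusted odds ratio would then contrast three or more vehicles with a mixture of one and two. That is not the effect of the program in the Intervention section, which calls MTR the newly introduced part of the bundle. Reported uptake would be too low, and so would any six-month trend built on the flag. Someone replicating the study from the protocol would build the wrong variable.

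**Working it through.** **Vehicle count**

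| Step | Source | Vehicles |
|---|---|---|
| Routine response | Study design and Setting | 1 |
| Added fire engine or basic life support team | Intervention | +1 |
| Basic MTR response | sum | 2 |
| Needed to be coded positive | Variables and measurement | 3 or more |

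Nothing in the documents leaves the routine ambulance out of the count. The rule counts all vehicles arriving under one accident number. Both named types are identified by the added tier, and neither implies a third vehicle.

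**Illustration of size**

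The plan states no figure to reproduce and gives no vehicle counts, so the inputs below are assumptions.

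- q1, q2, q3: shares of 2015–16 patients with one, two, and three or more vehicles.
- e: risk difference, three or more vehicles against one.
- f: fraction of e that a two-vehicle response carries.
- c: weight of single-vehicle responses. c = q1 if only 2015–16 is analyzed. c = 1 + q1 if all four years are pooled with an equal-sized, all single-vehicle before phase. The plan does not say which set the individual-program analyses use, so both are shown.

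Crude risk differences:

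- Written rule: e × [1 − f·q2/(c + q2)]
- Two or more: e × (q3 + f·q2)/(q2 + q3)

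Setting the two equal gives f* = (c + q2)/(c + 2·q2 + q3), which does not depend on e or the base rate. Above f* the written rule gives the smaller estimate; below it, the larger.

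| q1 / q2 / q3 | MTR coded negative, q2/(q2+q3) | Uptake: written vs two or more | f*, four years | f*, 2015–16 |
|---|---|---|---|---|
| 50/40/10% | 80.0% | 10% vs 50% | 0.792 | 0.643 |
| 40/50/10% | 83.3% | 10% vs 60% | 0.760 | 0.600 |
| 30/50/20% | 71.4% | 20% vs 70% | 0.720 | 0.533 |
| 20/50/30% | 62.5% | 30% vs 80% | 0.680 | 0.467 |

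For the third row, pooled: c = 1.3 and f* = 1.8/2.5 = 0.720. For 2015–16: c = 0.3 and f* = 0.8/1.5 = 0.533.

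**Worked example, third row, e = 2.0 points**

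The 2.0 points is 11% − 9%, the survival difference assumed under Sample size calculation for the whole bundle. It is not an MTR effect and serves only as a scale.

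- Pooled, f = 1: written 2.0 × (1 − 0.5/1.8) = 1.44; two or more 2.0 × 0.7/0.7 = 2.00.
- 2015–16, f = 1: written 2.0 × (1 − 0.5/0.8) = 0.75; two or more 2.00.

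| f | Pooled: written vs two or more | 2015–16: written vs two or more |
|---|---|---|
| 1 | 1.44 vs 2.00 | 0.75 vs 2.00 |
| 0.75 | 1.58 vs 1.64 | 1.06 vs 1.64 |
| 0.5 | 1.72 vs 1.29 | 1.38 vs 1.29 |

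These are crude differences. The planned model is adjusted and has random intercepts for ambulance station.

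**The case against.** The strongest reply is that the phrase is a slip. The protocol is loosely worded elsewhere (for example, DACP for DACPR), and naming each MTR type for a single added tier suggests that two vehicles were meant. In that case one phrase is corrected and no estimate moves. This is plausible, but the documents do not show how the data were coded, and this sentence is the only rule given.

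The vehicle mixes, f and the 2.0 points are also assumed, so the arithmetic says nothing about what happened in Seoul. That stands. The calculation shows only that the written rule can move the MTR estimate materially, and in either direction.

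The reach is limited too. The primary comparison uses study period. The link to the trend tests is conditional, because the key performance indicators named under Intervention concern dispatcher-assisted CPR. Both points stand.

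Finally, the Intervention section describes dispatch while the definition counts arrivals, so a second vehicle that was sent but did not arrive is missed under either threshold. That is a fair separate remark, and it does not rescue the threshold of more than two.

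**Conclusion.** The concern holds. The operational definition contradicts the program description, and no other section resolves it. Confidence is high about the contradiction; whether the data were actually miscoded cannot be told from the documents.

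If the written rule was applied, the MTR-specific results do not estimate the effect of the program described, and uptake is understated. The documents do not fix the size or direction of the error. Under the assumed mixes, the MTR risk difference is understated, relative to a two-or-more rule, only if a two-vehicle response carries more than 68–79% of the larger response's effect (four years pooled) or more than 47–64% (2015–16 only). Below those values it is overstated. The before/after comparison of outcomes is not affected. The point should be fixed because it concerns a program-level exposure and costs little to settle.

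**What to change.** First confirm from the analysis code which threshold was used. Then reconcile Variables and measurement with Intervention by defining MTR as positive when *two or more* vehicles arrived under the same accident number.

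- If the data were coded as two or more, correct the sentence only.
- If they were coded as three or more, recode from the existing dispatch and run-sheet records. Rerun the MTR absolute difference, the individual-program model and any MTR trend that uses the flag.

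No new data are needed, and neither the sample size nor the primary comparison changes. If benefit rises with the number of vehicles, the two-or-more estimate averages over ordinary and larger responses, which matches the program as described.

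### In the individual-program analyses, MTR is coded by vehicles that arrived although the program is a dispatch policy, so the MTR association can depend on how the arrest unfolds; for FCPR this is possible but not shown

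*Combined protocol and SAP*

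**What the plan says.** The Variables and measurement section sets both exposures by what happened after dispatch. For the multi-tier response: "The MTR was positive if more than 2 vehicles arrived to cases with the same accident number". For the feedback program: "FCPR was considered as positive if the corresponding ambulance used a defibrillator with feedback function".

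The Intervention section describes the programs at an earlier step. MTR works by "using the nearest available fire engine or basic life support vehicle team in addition to routine ambulance dispatch", which is a rule about what is sent. For the feedback program, "The FCPR program included the distribution of defibrillators with feedback functions to each ambulance and EMT training program", and "EMS personnel were also strongly encouraged to use a defibrillator with a feedback function". Before 2015, according to Study design and Setting, "only 27 (23.3%) were equipped with a defibrillator with a feedback function until December 2014". (27 of the 140 ambulances is 19.3%, not the printed 23.3%; nothing below depends on this.)

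Under Main outcomes, "The tertiary outcome was the prehospital return of spontaneous circulation (ROSC").

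Statistical analysis uses the exposure codes in two places: the absolute differences between patients who did and did not receive each program, and the mixed-effects logistic models for each program. Those models adjust for potential confounders that are not listed. The before/after comparison uses study period and does not use the codes. The plan has no dispatch-based coding, time-zero rule, landmark or sensitivity analysis for these exposures.

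**The concern.** Whether a further vehicle arrives is settled during the resuscitation. If ROSC comes early and the further unit is stood down, or the patient leaves before it gets there, the patient counts as MTR-negative although MTR was activated. A long resuscitation on scene gives the further unit more time to arrive. The MTR-negative group could then be enriched with patients whose prognosis was already good.

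Study design and Setting strengthens the point: crews may stop CPR in the field only for ROSC, so a resuscitation that ends early there is a favourable one. Early ROSC is not an exclusion under Study population. For prehospital ROSC the ordering problem is direct, because the outcome can occur before the exposure is determined.

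Adjusting for rhythm or witness status does not remove this dependence. Adjusting for scene time would not either, since scene time also reflects the course of the arrest. At stake is the plan's stated aim of estimating the individual effect of each program. The fault is separate from the vehicle-count threshold, because any threshold based on arrival has it.

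**Working it through.** The plan gives no figure for cancellations, ROSC timing or MTR prevalence, so there is nothing of its own to reproduce. The check asks how far the coding alone could move a null association.

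**Inputs**
- p, overall survival: 9% or 11%, the two rates assumed under Sample size calculation.
- d, share of patients with a further unit dispatched: assumed.
- s, share of dispatched patients who have early ROSC and, because of it, no recorded arrival: assumed.
- q, survival among those patients: assumed.
- No true MTR effect.

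**Formulas**
- MTR-positive survival = (p − s·q) / (1 − s)
- MTR-negative survival = [(1 − d)·p + d·s·q] / [(1 − d) + d·s]

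**Worked case**, p = 0.11, d = 0.70, s = 0.02, q = 0.40:
- MTR-positive: (0.11 − 0.008) / 0.98 = 10.41%
- MTR-negative: (0.033 + 0.0056) / (0.30 + 0.014) = 12.29%
- Odds ratio 0.83, where the truth is 1.00.

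**Varying the assumptions** (p = 0.11, q = 0.40)

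| d | s | MTR-positive | MTR-negative | OR |
|---|---|---|---|---|
| 0.70 | 0.02 | 10.41% | 12.29% | 0.83 |
| 0.70 | 0.05 | 9.47% | 14.03% | 0.64 |
| 0.50 | 0.02 | 10.41% | 11.57% | 0.89 |
| 0.50 | 0.05 | 9.47% | 12.38% | 0.74 |
| 0.35 | 0.02 | 10.41% | 11.31% | 0.91 |
| 0.35 | 0.05 | 9.47% | 11.76% | 0.79 |
| 0.70 | 0.002 | 10.94% | 11.13% | 0.98 |
| 0.70 | 0.005 | 10.85% | 11.33% | 0.95 |

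The rows with d = 0.35 apply if both phases are pooled, are equal in size and have no MTR before 2015: 0.70 / 2 = 0.35. Statistical analysis does not restrict the program models to the after phase. The last two rows apply if 2% or 5% of dispatched patients have early ROSC but only 10% of those lack an arrival: 0.10 × 0.02 = 0.002 and 0.10 × 0.05 = 0.005.

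**Wider grid.** Let 2–5% of patients have early ROSC with 50–70% survival, let 50–70% be dispatched MTR, and let 10–50% of the dispatched early-ROSC patients be coded negative. The odds ratio then runs from 0.98 to 0.57 at 9% survival and from 0.98 to 0.63 at 11%. If no such patient is miscoded, it is 1.00.

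**Prehospital ROSC as outcome.** Every miscoded patient has the outcome, so q = 1. With d = 0.70, s = 0.02 and an assumed overall ROSC rate of 10%, the formulas give 8.16% versus 14.01%, OR 0.55. At 20% they give 18.37% versus 23.57%, OR 0.73.

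**Scale.** The planned improvement from 9% to 11% is an odds ratio of (0.11/0.89) / (0.09/0.91) = 1.25.

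**The case against.** A reader might infer that early-ROSC patients do fall into the unexposed groups and that both program effects are biased. The documents do not support that.

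- **Cancellation and order of arrival.** Nothing says that further units are stood down after ROSC, or that the further unit arrives after the ambulance. A unit already sent that arrives after ROSC makes the patient MTR-positive, exactly as dispatch coding would, and adds no bias. The larger figures above treat every unit not yet present at ROSC as never arriving. This stands: the size may be negligible.
- **Direction.** This mechanism works against MTR. Early recognition by the dispatcher could favour MTR cases, and MTR is tied to calendar period. The net direction is not determined. This also stands.
- **Estimand.** The plan describes groups receiving each program, and an as-received contrast is legitimate. However, it does not estimate the effect of a dispatch policy, and it needs protection against an outcome that precedes the exposure. The plan has none.
- **FCPR.** The definition can be read at ambulance level. The Intervention section also says that all CPR processes were recorded by these devices. Primary rhythm is collected at the scene, which suggests that a monitor is attached early whatever follows. The visible driver of exposure is equipment: 27 ambulances before 2015, then distribution to each one. Use was encouraged rather than required, so selection by the crew is possible but not shown. Coding by carriage as the main exposure would approach study period, which is already analysed. This defeats a change of the main FCPR exposure.
- **Feasibility.** The sources under Data sources and collection are not said to record units dispatched but not arrived, or device-distribution dates. This needs checking and does not remove the MTR point.

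**Conclusion.** The point holds for MTR, as a possible bias confined to the individual-program analyses. Arrival coding does not match the dispatch policy it is meant to represent, it can depend on the course of the arrest, and for prehospital ROSC the outcome can come first.

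The size rests wholly on assumed prevalence, early-ROSC share, survival and miscoding. For the survival outcome a null odds ratio could move to between about 0.98 and about 0.6; for prehospital ROSC the shift could be larger. The mechanism alone acts against MTR, but the net direction of bias is uncertain.

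For FCPR the documents support only a sensitivity analysis and a clarification of what counts as use. The before/after estimate of the bundle is untouched by this coding.

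**What to change.** 1. **MTR main exposure.** Code MTR by whether a further unit was dispatched at the initial call under the same accident number, whether or not it arrived. Units requested later should not count, since such requests also depend on the arrest. Report arrival-based coding as a secondary, as-received analysis.
2. **Fallback.** If non-arriving units are not recorded, add a sensitivity analysis excluding patients with ROSC before second-unit arrival, where times exist. A patient with no second unit has no such time, so a common cut-off from the call should be fixed in advance and applied to both groups. Excluding early ROSC from the MTR-positive group alone would worsen the imbalance.
3. **FCPR.** State whether use is judged per patient or per ambulance. Add a sensitivity analysis by whether the responding ambulance carried a feedback defibrillator on that date.
4. **Vehicle count.** Reconcile the threshold with the Intervention section. Read literally, it requires three vehicles, while the program adds one unit to the ambulance.

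The cost is linkage to dispatch records, and to device-distribution dates for item 3, plus some dilution of the MTR effect from units sent that never arrived. Dispatch coding removes dependence on what happens after dispatch. It does not remove confounding by how readily the arrest was recognised, so the program models should list their covariates.
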